3.4 Outcomes

This trial will have two primary outcomes, one around essential components for ANC, and one for essential components for PNC.

Outcome 1 (ANC): Essential components included in the composite measure of integrated services specific to ANC visits are listed below.

- EC1 = Respectful maternity care indicators:
 - Introductions, greeting the woman, consent, questions
- EC2 = Screening for Pre-eclampsia:
 - Measure BP

- Test urine for proteinuria
- EC3 = Screening for, prevention and management of Anaemia:
 - Measure Haemoglobin
 - Provide ferrous sulphate with folic acid
- EC4 = Screening for, prevention and management of Malaria:
 - Checked for clinical symptoms and test for Malaria if relevant
 - Provide treatment if needed
 - Provide bed nets if not provided yet
 - Provide Intermittent Presumptive treatment
- EC5 = Screening for, prevention and management of HIV:
 - Test for HIV
 - Provide Prevention of mother to child transmission care (PMTCT)
 - Provide anti-retroviral drugs (ARV) for mother if needed
- EC6 = Screening for, prevention and management of Syphilis:
 - Test for syphilis
 - Provide antibiotics if needed
- EC7 = Screening for, prevention and management of Tuberculosis (TB):
 - Checked for clinical symptoms and test for TB
 - First line TB drugs or referral if needed
- EC8 = Prevention of Tetanus in mother:
 - Tetanus toxoid vaccination
- EC9 = Screening and counselling for mental health and domestic violence:
 - Screening tools
 - Counselling services
- EC10 = Estimation of BMI:
 - Assess maternal height
 - Assess maternal weight
- EC11 = Prevention of post- and pre-term birth:
 - Estimate gestational age
- EC12 = Assessment of foetal wellbeing during pregnancy, Screening for multiple pregnancy, abnormal lie and presentation during pregnancy:
 - Assess growth using fundal height measurement
 - Assess foetal heart rate (FHR)
 - Abdominal palpation
- EC13 = Provide advice on birth preparedness and danger signs of pregnancy:
 - Consultation

The outcome for each ANC visit will be a score which measures the proportion of the above components that was delivered during that visit (EC_ANC).

The score will measure the proportion of essential components delivered in full. All thirteen essential components listed above are applicable for ANC. Some essential components

involve multiple components, at least one of which is always applicable; some components are only applicable to a subset of clients, eg HCP counsels the woman about mental health is only applicable if the client's response to a previous question is cause for concern. All essential components will carry a weight of 1. The overall score will be derived by aggregating the weighted scores for each essential component which will then be converted to a percentage. Six essential components are binary; hence the score can only be 0 (not achieved), or 1 (achieved and single weighted); in some cases the determination of this involves an algorithm. The other seven essential components are not binary as they have sub-components assessed independently and thus may be partially achieved and carry an intermediate score, eg a multiple of 0.25 for essential component 1 (respectful maternal care).

Outcome 2: Essential components included in the composite measure of integrated services specific to PNC visits are listed below.

- EC1b = Respectful maternity care indicators:
 - Introductions, greeting the woman, consent, questions
- EC2b = Screening for Pre-eclampsia:
 - Measure BP
- EC3b = Screening for, prevention and management of Anaemia:
 - Measure Haemoglobin
 - Provide ferrous sulphate with folic acid
- EC4b = Screening for, prevention and management of Malaria:
 - Checked for clinical symptoms and test for Malaria if relevant
 - Provide bed nets if not provided yet
- EC5b = Screening for, prevention and management of HIV:
 - Test for HIV
 - Provide Prevention of mother to child transmission care (PMTCT)
 - Provide anti-retroviral drugs (ARV) for mother and baby
- EC6b = Screening for, prevention and management of Syphilis:
 - Test for syphilis
 - Provide antibiotics if needed
- EC7b = Screening for, prevention and management of Tuberculosis (TB):
 - Checked for clinical symptoms and test for TB
 - First line TB drugs or referral if needed
- EC8b = Prevention of Tetanus in mother and baby:
 - Tetanus toxoid vaccination
- EC9b = Screening and counselling for mental health and domestic violence:
 - Screening tools
 - Counselling services
- EC10b = Provide advice and support regarding breastfeeding:
 - Consultation

- EC11b = Offer postpartum contraception:
 - Consultation
- EC12b = Monitor newborn growth:
 - Weigh the baby
- EC13b = Clinical examination of the mother:
 - Examine the mother
- EC14b = Clinical examination of the baby:
 - Examine the baby
- EC15b = Immunization status checked and required vaccinations offered and provided if required
- EC16b = Provide advice on danger signs in the mother and baby:
 - Consultation

The outcome for each PNC visit will be a score which measures the proportion of the above components that was delivered during that visit (EC_PNC). This score will be derived in a similar manner to the score for ANC, the difference being that three essential components used for ANC will be dropped and six others added.

The observation tool is detailed in **Appendix 2**.

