Appendix 1: ANC and PNC - essential components of care packages

Signal Functions	Essential components	Essential equipment and consumables and other ¹
FOR BOTH ANC AND PNC		
1. Screening for pre-eclampsia	Measure BP	BP machine and stethoscope
	Test urine for proteinuria	Urine dip-stix, urine containers
2. Screening for, prevention, and, management of	Measure Haemoglobin (Hb)	HemoCue machine and cuvettes, or laboratory measurement of HB e.g. coulter counter or HB colour chart
Anaemia	Provide ferrous sulphate with folic acid	Ferrous sulphate tablets (preferably combined with folic acid) – any formulation for oral intake – adult dose
3. Screening for, prevention, and, management of Malaria	Test for malaria	Thermometer Malaria rapid test, or, malaria microscopy done in lab
	Provide bed nets	Bed nets
	Provide Intermittent Presumptive Treatment (IPT)	Sulphadoxine – Pyramethamine (SP) or equivalent antimalarial tablets
4. Screening for, prevention,	Test for HIV	HIV test kit – (single or with syphilis combined)
and, management of HIV	Provide Prevention of mother to Child Transmission Care (PMTC)	Drugs ²
	Provide anti-retroviral drugs (ARV) for mother and baby	Drugs ²

¹ Assumes availability of non-sterile gloves, needles, syringes or capillary tubes, skin swabs, tourniquet and cotton wool available.

² All drugs as per national protocol – to be identified for each country

Signal Functions	Essential components	Essential equipment and consumables and other ¹
5. Screening for, prevention,	Test for syphilis	Rapid test for syphilis (preferred dual with HIV – rapid test)
and, management of Syphilis	Provide antibiotics	Procaine Penicillin for i.m. use
6. Screening for, prevention and management of Tuberculosis (TB)	Test for TB (sputum Ziehl-Neelsen stain or Gen expert point of care testing)	Sputum pots, Lab for sputum Ziehl-Neelsen staining or Gen expert point-of-care testing
(15)	First line TB drugs	Drugs ²
	BCG vaccination for newborn	BCG vaccination
7. Prevention of Tetanus in mother and baby	Tetanus toxoid vaccination	Tetanus toxoid vaccination
8. Prevention of Hepatitis B	Hep B vaccination	
9. Screening and counselling for	Screening tools	EPDS or other Screening tool for Mental health
mental health and domestic violence	Counselling services	Screening tool for domestic violence
Violence		Referral pathway for counselling
FOR ANC ONLY		
10. Estimation of BMI	Assess maternal height	Height measure
	Assess maternal weight	Weighing scale (adult)

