(or the woman already		
declared it herself)	0 - No, 1 – Yes	
If the woman had a		
companion with her, was		
the companion allowed to		
be with the pregnant		
woman during ANC	0 - No, 1 - Yes, -88 - Not	
consultation?	applicable (no companion)	
RMC subcomponent 3		0.25
The HCP asked how the		
pregnant woman was and		
asked about any problems	0 - No, 1 - Yes,	
RMC subcomponent 4		0.25
The HCP explained to the		
woman what they would		
like to do, prior to all		
examination or		
investigation	0 - No, 1 - Yes,	
The HCP explained that the		
findings of any		
examination and/or		
investigation would be	0 - No, 1 - Yes, -88 - Not	
confidential	applicable (no testing)	
The HCP explained the		
findings of investigations		
or examinations to the		
woman	0 - No, 1 – Yes	

EC2 = Screening for,			1
prevention and			
management of Anaemia			
Anaemia subcomponent 1			0.5
Blood taken to test	0 - No, 1 - Yes		
haemoglobin level	•		
If yes, HCP recognised and	0 - No, 1 – Yes, -88 Not		
acted upon abnormal	applicable		
findings			
Anaemia subcomponent 2			0.25
Iron tablets and folic acid	0 - No, 1 - Yes		
were given or prescribed			
for the pregnant woman			
Anaemia subcomponent 3			0.25
HCP counselled the	0 - No, 1 - Yes		
woman about dietary			
sources of iron			
Anaemia: Not in scoring			
If the woman was referred,			
what was the reason?	comment		
EC3 = Screening for Pre-			1
eclampsia			
Preeclampsia			0.5
Subcomponent 1			
The pregnant woman had			
her BP measured and			
noted in booklet	0 - No, 1 - Yes	0.1.	
If BP over 140/90 mmHg,		Only to	
HCP recognised and acted		appear if	
upon abnormal findings		answer to	
	0 - No, 1 – Yes, -88 – Not	previous question = 1-	
	applicable (BP normal)	Yes	
Preeclampsia	applicable (Br Hormal)	163	0.5
Subcomponent 2			0.5
The HCP checked urine for			
protein and noted in			
booklet	0 - No, 1 - Yes		
If yes, HCP recognised and	, , , , , , , , , , , , , , , , , , ,	Only to	
acted upon abnormal		appear if	
findings		answer to	
		previous	
		question = 1-	
	0 - No, 1 - Yes	Yes	
Preeclampsia: Not in			
scoring			
If the woman was referred,			
what was the reason?	comment		

EC4 = Screening for,			1
prevention and			
management of Malaria			
Malaria Subcomponent 1			0.5
HCP gave her the SP		Only to	
		appear if after	
	0 - No, 1 - Yes	1 st trimester	
HCP explained why it was		Only to	
important taking the SP		appear if	
		answer to	
		previous	
		question = 1-	
	0 - No, 1 - Yes	Yes	
HCP asked the woman			
whether she has			

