well being (or listened if			
she raised it)	0 - No, 1 – Yes		
If the woman expressed		Only to	
concern about her		appear if HCP	
psychological well-being,		asked or	
ie depression or anxiety,		woman raised	
the HCP counsels the		it	
woman	0 - No, 1 – Yes		
If the woman expressed		Only to	
concern about her		appear if HCP	
psychological well-being,		asked or	
ie depression or anxiety	0 - No, 1 - Yes, -88 - Not	woman raised	
the HCP refers the woman	Applicable (No concerns	it	
for additional support	expressed)	10	
Mental subcomponent 2	Слргеззеці		0.5
HCP asked the woman if			0.5
she is experiencing	0 No 1 Yes		
domestic abuse	0 - No, 1 – Yes	0.1.	
If the woman expressed		Only to	
concern about domestic		appear if HCP	
abuse, the HCP counsels	0 - No, 1 - Yes, -88 - Not	asked or	
the woman	Applicable (No concerns	woman raised	
	expressed)	it	
If the woman expressed		Only to	
concern about domestic		appear if HCP	
abuse the HCP refers the	0 - No, 1 - Yes, -88 - Not	asked or	
woman for additional	Applicable (No concerns	woman raised	
support	expressed)	it	
EC10 = Estimation of BMI			1
If subsequent visit, HCP		Only to	
checked if BMI previously		appear if	
recorded		subsequent	
	0 - No, 1 - Yes	visit	
BMI measured by HCP and	,	If ANC1: This	
noted		is the first	
		question to	
	If ANC1, answers are only	appear	
	= 0 - No, 1 – Yes	аррсаі	
	- 0 - NO, 1 - 165	If subsequent	
	If subsequent visit answers	visit, this is	
	•	the second	
	are = 0 - No, 1 - Yes		
	, -88 - Not applicable (BMI	question to	
If DMI do 40, LICD	already noted)	appear	
If BMI under 18, HCP	0 No 4 Var 00 No		
recognised and acted upon	0 - No, 1 - Yes-88 - Not		
abnormal findings (e.g.	applicable (BMI normal or		
provided nutrition advice	unchecked)	l	I

I	I	I	I .
and supplementation, or			
referred if signs of gravity)			
If BMI over 30, HCP	0 - No, 1 - Yes-88 - Not		
provided nutrition advice	applicable (BMI normal or		
	unchecked)		
EC11 = Prevention of post-			1
and pre-term birth			
HCP noted the gestational			
age in booklet	0 - No, 1 - Yes		
EC12 = Assessment of			
foetal wellbeing during			
pregnancy; Screening for			
multiple pregnancy,			
abnormal lie and			
presentation The HCD measured		Onlyannas	
The HCP measured		Only appears	
symphysis- fundal height		if age of pregnancy >	
	O No 1 Ves		
If fundal haight magazired	0 - No, 1 - Yes 0 - No, 1 - Yes, -88 - Not	16 weeks	
If fundal height measured,			
HCP recognised and acted	applicable (no abnormal		

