HCP checked the perineum	0 - No, 1 - Yes	
to look for scar of any	,	
perineal tear and/or		
episiotomy performed		
HCP checked the abdomen	0 - No, 1 - Yes	
to see if any wound from	,	
caesarean section		
HCP recognised and acted	0 - No, 1 - Yes, -88 - Not	
upon abnormal findings	applicable (no abnormal	
with abdominal or	findings)	
perineum examination		
Mother exam		0.5
Subcomponent 3		
HCP asked about urination	0 - No, 1 - Yes	
and urinary continence		
HCP asked about bowel	0 - No, 1 - Yes	
function		
HCP asked the woman	0 - No, 1 - Yes	
about signs of Deep vein	0 110, 1 100	
thrombosis in her legs		
HCP gave the woman	0 - No, 1 - Yes	
hygiene advice	,	
HCP recognised and acted	0 - No, 1 - Yes, -88 - Not	
upon abnormal findings	applicable	
EC14b = Clinical		1
examination of the baby		
HCP observed hygiene	0 - No, 1 - Yes	
measures before		
examining the baby		

Have the newborn's eyes	0 - No, 1 - Yes	1	 
been checked?	0 - 100, 1 - 163		
Was the temperature of	0 - No, 1 - Yes		
the newborn taken with a	0 - 100, 1 - 163		
thermometer?			
Has the HCP listened to	0 - No, 1 - Yes		
the heartbeat of the	0 - 100, 1 - 163		
newborn (auscultation)?			
Did the HCP examine the	0 - No, 1 - Yes		
abdomen of the newborn	0 - 100, 1 - 163		
(palpation)?			
Has the HCP checked the	0 - No, 1 - Yes		
umbilical cord of the	0 140, 1 163		
newborn?			
Has the HCP checked if the	0 - No, 1 - Yes		
newborn is passing urine	1, 2		
Has the HCP checked if	0 - No, 1 - Yes		
the newborn has passed	1, 2		
stools or opened its			
bowel?			
Has the newborn been	0 - No, 1 - Yes		
weighed?			
HCP completed the baby's			
growth chart			
	0 - No, 1 - Yes, -88 - Not		
HCP recognised and acted	applicable (no abnormal		
upon abnormal findings	findings)		
EC15b = Immunization			1
status checked and			
required vaccinations			
offered and provided			
HCP checked whether	0 - No, 1 - Yes		
newborn vaccines are up-			
to-date			
HCP offered appropriate	0 - No, 1 – Yes, -88 Not		
vaccination	applicable		
EC16b = Provide advice on			1
danger signs in the			
mother and baby			
HCP gave advice on	0 - No, 1 - Yes		
danger signs (i.e. signs that			
indicate the baby is sick) to			
look out for in the baby			
HCP gave the date of the	0 - No, 1 - Yes	Does not	
next PNC contact to the		appear if PNC	
mother		visit = W6	
Woman departure/exit	[enter time]		
time			
Comments	[free text]		

SCORING EXAMPLE: Respectful Maternity Care essential component

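### The PNC immunisation component (EC15b) is defined as vaccination offered and provided, but the checklist scores only a status check and an offer

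*Protocol*

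**What the plan says.** Section 3.4 of the Protocol sets two primary outcomes, one for ANC visits and one for PNC visits. Each is a score for the share of essential components delivered. The PNC score has 16 components. One of them, EC15b, is defined as "Immunization status checked and required vaccinations offered and provided if required".

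Appendix 2 holds the observation checklist from which the score is built. Its EC15b heading repeats that vaccinations are to be both offered and provided, and gives the component 1 point. Two rows follow:

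- a row beginning "HCP checked whether", on whether the newborn's vaccines are up to date, answered no or yes;
- a row beginning "HCP offered appropriate", on vaccination, answered no, yes or not applicable.

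The next heading after these is EC16b. The introduction to Appendix 2 says that credit is given when all applicable questions have been observed.

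**The concern.** The definition has three acts: check, offer, provide. The instrument records two. An act with no row cannot affect the score, so for this item the score cannot tell a visit that ended with a vaccine given from one that ended with an offer only.

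This matters for two reasons. First, section 3.4 says the score measures components delivered in full, and for EC15b it does not. Second, the Protocol expects supply to show in the outcome. Section 3.2.3 plans to use availability data to assess how equipment and consumables affect delivery, and the paragraph on shortages just before section 5 expects a shortage to be visible in what is observed. A provider who checks, offers and has no vaccine in stock still scores 1, so EC15b hides the situation those passages want to capture. Appendix 3 would record absence of BCG vaccine, but by facility and period, not by visit.

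**Working it through.** **Inputs.** 13 ANC and 16 PNC components, each with weight 1 (section 3.4 and the introduction to Appendix 2). EC15b has two rows (Appendix 2). The simulations use an effect of 0.1, and the stated detectable difference is 0.23 (section 3.6).

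**Component count.** Section 3.4 says the PNC list drops three ANC components and adds six: 13 − 3 + 6 = 16. This reproduces the stated total.

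**Row by row.** Every possible course of a PNC visit, scored from the two rows and set against the definition:

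| Visit | Checked row | Offered row | Score | Definition met? |
|---|---|---|---|---|
| Status checked, nothing due | yes | not applicable | 1 | yes |
| Due, checked, offered, given | yes | yes | 1 | yes |
| Due, checked, offered, not given | yes | yes | **1** | **no** |
| Due, checked, not offered | yes | no | 0 | no |
| Not checked | no | any | 0 | no |

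Only the third case is misclassified. The scoring rule in Appendix 2 is worded for subcomponents and EC15b has none. The table assumes the same all-applicable rule holds for the component as a whole. A different algorithm would not remove the gap, since no row holds the missing information.

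**Is the omission a convention of the tool?** No. Other components do have rows for provision: tetanus vaccination (EC8 and EC8b), bed nets (EC4 and EC4b), iron and folic acid at PNC, where prescribing and providing have separate rows, and contraception, where provision or referral is recorded.

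**Size at one visit.** Weight / number of components = 1/16 = 0.0625, or 6.25 percentage points. That is 0.0625/0.1 = 62.5% of the simulated effect and 0.0625/0.23 = 27% of the stated detectable difference. It is a ceiling for a single visit, not an estimate.

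**Size on average.** Let q be the share of observed PNC visits in the third case. The mean PNC score is too high by q/16. The Protocol gives no value for q, so these are assumptions:

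- q = 0.1: 0.1/16 = 0.006
- q = 0.3: 0.3/16 = 0.019
- q = 1: 1/16 = 0.0625

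**Size on the training effect.** The shift is (q after training − q before training)/16. It is zero if q does not change. It is positive if training raises offers more than vaccines given, and negative if training closes the gap. An assumed rise in q of 0.3 gives +0.019, which is 0.019/0.23 = 8% of the detectable difference. An equal fall gives −0.019. Nothing in the Protocol fixes the sign.

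**The case against.** The best defence is that the tool is the same before and after training, so a shared omission does not by itself bias the comparison. That stands. The defence may add that checking and offering are what a provider controls, that giving the vaccine depends on stock, and that credit is not for an offer alone because status must also be checked. These are fair points. They would support defining EC15b as checked and offered, but the Protocol defines it otherwise, in section 3.4 and again in the tool's own heading.

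A reader might infer a wider fault covering two more components. The documents do not support that.

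- **Mental health (EC9).** The ANC row on psychological "well being (or listened if" the woman raised it herself might look like credit without screening, given that section 3.4 lists screening tools and Appendix 1 names "EPDS or other Screening tool for Mental health". But that entry is in the Appendix 1 column for equipment and consumables, so it describes what should be available. Section 3.4 illustrates this component with a question and the client's reply. If concern is voiced, counselling and referral rows must still be met, so disclosure alone does not earn the 0.5. The greeting and companion rows also give credit when the woman speaks first, which suggests a deliberate convention.
- **Respectful care (EC1, EC1b).** Section 3.4 summarises this as "Introductions, greeting the woman, consent, questions", and no visible row records permission. But subcomponent 4 requires the provider to explain what they would "like to do, prior to all" examination or investigation, and this can reasonably stand for consent. The scoring example for this component at the end of Appendix 2 was not readable here. At most this is a point of wording.

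**Conclusion.** The point holds for EC15b only. Section 3.4 and the Appendix 2 heading require provision, the rows do not record it, and a full point, 6.25 percentage points of a PNC visit score, can be earned with no vaccine given. The average overstatement is q/16, with q unknown.

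A reader might go on to infer that the estimated training effect is inflated, or that the score fails to measure the PNC outcome. Neither follows. The effect on the training estimate could be zero or have either sign, and one missing row among 16 components leaves most of the score untouched. The ANC outcome is not affected, and no sample size, power or detectable-difference figure changes. This is a modest mismatch between a primary outcome and its instrument, worth correcting because the correction is specific and cheap. It rests on the visible rows being the whole of EC15b and on credit requiring all applicable rows.

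**What to change.** Before launch, add one row to EC15b in Appendix 2 recording whether the required vaccine was provided at the visit. Give it a not-applicable answer for visits where none was due, state how refusal is coded, and require the row for the point. Keeping the offer row as well would let offers without provision be counted and compared with the availability data.

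If provision is not meant to be scored, or cannot be observed in the consultation, reword section 3.4 and the EC15b heading to say checked and offered. If observation has already started, only this rewording is open for visits already recorded, because provision cannot be recovered from the existing rows.

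For EC1 and EC1b, one sentence in section 3.4 stating that the explanation row in subcomponent 4 is the measure of consent would be enough. EC9 needs no change on this account.

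The cost is one extra row in the electronic form, a line in observer training, and lower baseline EC15b scores wherever offers now exceed vaccines given.

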11. Prevention of post- and	Estimate gestational age	Pregnancy wheel
pre- term birth		Ultra sound scan at secondary/tertiary level
	Assess growth using fundal height measurement	Tape measure (with centimetres indicated)

Signal Functions	Essential components	Essential equipment and consumables and other ¹
12. Assessment of fetal wellbeing during pregnancy	Assess Fetal Heart Rate (FHR)	Pinard stethoscope or Doptone
13. Screening for multiple pregnancy, abnormal lie and presentation during pregnancy	Obstetric palpation	Ultra sound scan at secondary level
14. Provide advice on birth preparedness and danger signs of pregnancy	Consultation	Patient information material available on hand-held card or posters in health care facility or patient leaflets
15. Screening and management of gestational diabetes ³	Measure blood glucose Provide dietary advice	Glucometer (can be combined with Hb measurement) Patient information material available on hand-held card or posters in health care facility or patient leaflets
FOR PNC ONLY		
16. Provide advice and support regarding breast-feeding (BF)	Consultation	BF advised (when not contra-indicated) Awareness of contra-indications among staff
17. Offer post-partum contraception	Consultation	IUD, progesterone only pill, Depo Provera, condoms
18. Monitor newborn growth	Weigh the baby	Weighing scale (baby), weight monitoring chart

³ Optional possibly not universal and screening may be only for women considered at-risk, check with national guidelines

Signal Functions	Essential components	Essential equipment and consumables and other ¹
19. Clinical examination of the mother and baby	Examine the mother and baby	Examination area, couch
20. Provide advice on danger signs in the mother and baby		Patient information material available on hand-held card or posters in health care facility or patient leaflets

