Appendix 2: Tools for data collection for observation

Below is the observation checklist. Essential components are numbered slightly differently than appendix 1 for the construction of the score. The scoring attributes will not appear for the data collectors and only be used by the statistician at time of analysis. Each essential component is score 1, for a total of 13 essential components for ANC visits, and 16 for PNC visits. Essential components can be a sum of x number of subcomponents as indicated in the table. Each subcomponent needs all applicable questions to be observed (Please see examples of algorithms at the end of appendix).

Please note this tool is to be deployed on an electronic platform, therefore the formatting of the tool will be visually different to what is included here. All boxes starting with "If" will only appear depending on the answer to the relevant condition (e.g. treatment will only be asked for women tested positive). The "Not applicable" answer is available for questions which depend on the gestational age and type of visit. The tool will be deployed in FRENCH.

OBSERVATION

Variable label	Answers	Conditionality	Scoring
GENERAL			
Please select the region	[dropdown menu]		
Please select the name of the facility	[dropdown menu]		
If 'Other' facility, please specify	[free text]		
Date of survey	[select from calendar]		
Name of person completing form	[free text]		
Anonymous ID of HCP	[free text]		
ANC			
ANC general information			
First/subsequent contact	0 - Subsequent contact, 1 - first contact -99 INF		
Which subsequent visit was it?	2- ANC2, 3- ANC3, 4- ANC4, 5- ANC5, 6-ANC6, 7- ANC7, 7-ANC8	Only to appear if previous answer = 0 – Subsequent visit	
Gestational age (weeks)	[integer]		
Who gave information about gestational age	1 - Woman, 2 - Healthcare provider, 3 - Other (specify)		
If other, specify	[free text]		
Women arrival time in the facility	[time]		
Comments	[free text]		

ANC contact		
EC1: Respectful maternity		1 (sum of all
care		subcomponents)
RMC subcomponent 1		0.25 (Points given if all applicable questions are observed)
The healthcare provider		
(HCP) introduced		
themselves to the		
pregnant woman	0 - No, 1 - Yes	
The HCP greeted the		
pregnant woman (or		
answered if woman		
greeted first)	0 - No, 1 – Yes	
RMC subcomponent 2		 0.25
The HCP asked the		
pregnant woman to take a	0 - No, 1 - Yes, -88 - Not	
seat	applicable (no chairs)	
The HCP asked the		
pregnant woman if she		
came with a companion		

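### PNC component EC16b is defined as danger-sign advice for mother and baby, but its block in the observation tool scores only advice about the baby and an appointment date

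*Protocol*

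**What the plan says.** Protocol section 3.4 defines the last PNC component as "EC16b = Provide advice on danger signs in the mother and baby", describes it only as a consultation, and refers to Appendix 2 for the tool. Appendix 1 has the same scope: "20. Provide advice on danger signs in the mother and baby".

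The Appendix 2 block keeps the mother-and-baby heading (it opens "EC16b = Provide advice on"), carries a score of 1, and has no subcomponents. It has two rows:

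- Danger-sign advice, with the signs explained as those that "indicate the baby is sick) to" watch for; the row ends "look out for in the baby".
- A row beginning "HCP gave the date of the", which asks whether the mother was told when to come for her next PNC visit. It does not appear at the week-6 visit.

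On weighting, section 3.4 says "All essential components will carry a weight of 1", and Appendix 2 says "Each essential component is score 1, for a total of 13 essential components for ANC visits, and 16 for PNC visits". Appendix 2 also says that a subcomponent earns credit only when every applicable question in it is observed.

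**The concern.** The two definitions name two recipients of danger-sign advice. The form on which the outcome is recorded asks about one of them and adds an item that belongs to neither definition.

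This matters because Appendix 2 is the data-capture form. If maternal danger-sign advice is not recorded at the visit, no later scoring rule or analysis plan can recover it. A provider who begins advising mothers on their own danger signs after training gains nothing in EC_PNC for doing so. A provider who advises on the baby only can receive full credit for a component described as covering both.

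**Working it through.** **Step 1. The plan's own count.** Section 3.4 lists EC1b to EC16b, which is 16 components. Its description of the PNC score as the ANC score with three components dropped and six added gives 13 − 3 + 6 = 16. Appendix 2 also states 16, so the figure reproduces.

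**Step 2. Weight of EC16b.** Each component scores 1, so EC16b is 1/16 = 0.0625, or 6.25 percentage points of EC_PNC at each visit.

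**Step 3. Is maternal danger-sign advice recorded elsewhere?**

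- EC13b (Appendix 2) covers examination of the mother, questions about symptoms and hygiene advice. None of this is danger-sign advice, and it is scored separately.
- Appendix 3 item da061 records whether the facility offered postnatal danger-sign advice, not whether it was given at an observed visit. It is not part of EC_PNC.
- In the copy of the protocol read here, part of the tool from EC9b to about EC12b is not legible. The EC16b block is complete, from its heading to the exit-time row.

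**Step 4. Tool against definition.** Two assumptions are needed. The definition is taken to need advice on both mother and baby. The tool is taken to need every applicable row, that is, baby advice and, before week 6, the date. Over all combinations of the three items, tool and definition disagree only here:

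| Visit | Baby advice | Maternal advice | Date given | Tool | Definition | Error in EC_PNC (points) |
|---|---|---|---|---|---|---|
| Before week 6 | yes | no | yes | 1 | 0 | +6.25 |
| Before week 6 | yes | yes | no | 0 | 1 | −6.25 |
| Week 6 | yes | no | row hidden | 1 | 0 | +6.25 |

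With the other items held fixed, switching maternal advice on or off never changes the tool score. If the point were instead split equally between mother and baby (an assumption; the protocol gives no split), the unrecorded maternal half would be 0.5/16 = 1/32 = 3.125 points.

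**Step 5. Effect on the intervention estimate.** Let d be the tool score minus the definition score for EC16b at a visit (−1, 0 or +1). In a simple before-and-after comparison, the error in the estimated effect is

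(mean d after training − mean d before training) / 16.

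If mean d is the same before and after, this is 0. As an illustration only, a fall in mean d from 0.50 to 0.25 gives (0.25 − 0.50)/16 = −0.016, an understatement of 1.6 points. The protocol has no data on this item from which to estimate either mean.

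**Step 6. Scale.** Section 3.6 simulates an effect of 0.1 and gives a detectable difference of 0.81 × 0.28 = 0.227, stated as 0.23. None of the inputs to that calculation depends on EC16b.

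**The case against.** The strongest reply has four parts.

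**The date row may be deliberate.** The ANC tool also scores a next-contact date, inside EC13, and section 3.4 leaves the detail of EC16b to Appendix 2. This stands in part: the documents do not show that the date must be unscored. But in ANC EC13 danger-sign advice is a separate 0.5 subcomponent and the date sits in the other one, so the ANC tool does not make danger-sign credit depend on the date.

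**A score of 0 for a missing date is inferred.** The rule requiring every applicable question is worded for subcomponents, and EC16b has none. Section 3.4 also says that some binary components use an algorithm, and the worked scoring example at the end of Appendix 2 is not legible here. This stands. A zero is the likely reading, not a stated one. The absence of a maternal row does not depend on it.

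**The effect on the trial result is small.** This also stands. It is one component of 16 in one of two primary outcomes. Disagreement that is constant over training cancels, and the errors have opposite signs and can partly offset.

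**The maternal item might lie in the illegible part of the tool.** This cannot be excluded for other components. It does not explain the EC16b block, which is complete and carries the mother-and-baby heading.

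A reader might also infer three stronger things that the documents do not support:

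- That training which only prompts a return date would raise the score. On the likely scoring rule a date earns nothing unless baby advice is also given, and at week 6 the row is absent.
- That 6.25 points against the 0.23 detectable difference (6.25/23 = 27%) measures bias. The first is an error in a score level and the second a difference between conditions; only a change in disagreement carries over.
- That the trial will report a result for maternal danger-sign advice. Section 3.8 plans analysis of the composite proportion, not of EC16b alone.

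**Conclusion.** The mismatch is real: the EC16b block does not measure half of what section 3.4 and Appendix 1 say the component contains, and it includes an item they do not mention. On the legible text, maternal danger-sign advice cannot move EC_PNC.

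The size is bounded at 6.25 points for any single visit. How much of that reaches the intervention effect depends on whether the disagreement changes with training, which the protocol gives no means of estimating. The finding concerns the content validity of one component of the PNC primary outcome. It rests on the EC16b block being complete as read; the figures for individual visits also rest on the all-rows-required reading. It is worth correcting because it cannot be repaired once observation has started.

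**What to change.** Before the first observation, add a scored row to Appendix 2 EC16b for danger-sign advice about the mother, next to the existing row about the baby. State whether the next-appointment date counts towards this component; if it does not, keep it as a recorded but unscored row. State how the rows combine into the single point, for example all required or split between mother and baby, and apply the week-6 exception explicitly. Section 3.4, Appendix 1 and the tool would then agree.

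If the sponsor intends the narrower content, the alternative is to amend the section 3.4 and Appendix 1 definitions to match the tool, but maternal advice would then be outside the outcome by design.

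The cost is one extra row and a scoring note in an electronic form, with a line in the data collectors' training. The visit is already being observed, and the sample size does not change.
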